Studies suggest that errors made during training improve later performance of the task. For example, in a study in which elderly subjects practiced rhythmic motion of the upper limb with and without visual feedback, greater errors made during treatment led to more movement improvement following training (Levy-Tzedek 2017). This result is consistent with the TCT as muscle activation is regulated by the difference between the actual limb position and referent limb position specified by the brain. The referent position also plays a role in the perception of the actual limb position, while the afferent component identifies the deflection of the limb from the referent limb position. Based on this combination, the system identifies the movement error, i.e., deviation of the limb from the target position. Movement correction is accomplished by properly adjusting the referent limb position.

The sensitivity of referent control may be enhanced by augmentation of the movement error, i.e., Joint Error Augmentation (JEA). Furthermore an improvement in referent limb control is likely to be associated with improvement in threshold (referent control) at the level of individual joints. Development of rehabilitation treatment protocols based on motor control theory, such as that underlying JEA, is a promising direction for robotic rehabilitation therapy.

Research Objectives:

Our goals are to investigate the effect of JEA on motor learning in healthy subjects and on upper limb rehabilitation in subjects with stroke.

Hypothesis 1: In both groups, JEA applied to the elbow joint range will lead to better learning of movement speed and precision of a reaching task compared to no JEA.

Hypothesis 2: In patients with stroke, JEA applied to the elbow joint range will lead to a greater increase in the patient's active control zone at the elbow compared to no JEA and thus in his/her ability to perform isolated voluntary movement of the elbow.

Research plan

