In our preliminary proof of principle study, we developed and tested a passive robotic system in 21 healthy subjects (aged 26.2, SD 1.2 yrs). A passive robotic arm was developed for supporting and monitoring arm motion and combined with a simple virtual reality pick-and-place game (Srör et al. 2018). Software was developed for integrating input from the robotic arm and a Kinect camera. The software includes a pick-and-place VR game, game success feedback, and motion feedback with and without JEA. Individuals were assigned to a training group with or without EA and performed one 30 min training period. There was no difference between groups in terms of the success rate of hitting the targets. The group training with EA tended to work longer and be more motivated. The application was found to be acceptable to healthy individuals, to enhance motivation to exercise and not to cause fatigue or any adverse effects (Srör et al., 2018; 2019a; 2019b).

The next phases of the study are to investigate the effects on learning with JEA feedback in healthy subjects, and then to test the JEA feedback effect in patients with stroke.

In two separate studies, we will test 24 healthy subjects and 24 patients who have moderate-to-severe stroke (spasticity + some arm movement). Testing of the healthy subjects will be done in Canada and testing of patients will be done in two countries (Israel-Soroker Hospital, Beer-Sheva; Canada-Jewish Rehabilitation Hospital, Laval/Montreal). The motivation for testing the application in patients at two sites is to assess the feasibility of conducting a multi-site study using this technology.

In both studies: Subjects will be randomly allocated to two equal groups. One group (control) will receive regular feedback and the other group will receive JEA feedback (randomized with catch trials).

Subjects will perform ~30 min of target reaching with their non-dominant/affected arm, 3 times in one week, with a minimum of 1 day between sessions. Rest periods will be provided when needed to avoid subject fatigue. In the experimental group, target locations will be tailored to coincide with active control range limits determined at the beginning of each session. In the stroke group, workspace extensions will be added as active range increases (i.e., exercise progression) for patients receiving JEA feedback.

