we will use a small (i.e., 10°) instead of a large error, to decrease direct perception of elbow position and conscious correction. Feedback in the form of task success of endpoint (hand) movement is presented at the end of each reaching trial to increase motivation and engagement (Guadagnoli and Lee 2004). The introduced error causes the subject to perceive their hand position as undershooting the target. The subject's task is to solve the problem of moving the arm further by learning to incorporate more elbow extension into the whole arm reaching task. Multiple solutions are needed in order to solve problems for targets located in different parts of the arm workspace. **Game difficulty** will be progressed according to the Challenge Point theory of motor learning (Guadagnoli and Lee 2004), which suggests that learning is enhanced by optimally challenging the individual through manipulation of task difficulty according to their motor skill level and cognitive capacity. Difficulty level will be increased by altering target locations (i.e., based on changes in active ranges for the JEA stroke group and by increments of 2 cm for the non-JEA group) and by decreasing the allowable movement time for each reach (increasing movement speed). Difficulty will be progressed when the participant reaches a 90% success rate. Low-cost motion tracking is used for clinical accessibility. **Motion tracking** is based on the Kinect II skeleton and an extended Kalman filter (Simon 2006) to improve accuracy (Fig. 3). A Kalman filter has two steps in each iteration. First, a prediction is made based on the current location and the motion model. The prediction is of both the state variables and their uncertainty. Then, the predictions are updated based on the current measurement using a weighted average, which incorporates the uncertainties of the measurements and the predicted states. The model assumes no shoulder motion, and motion along the same direction as in the previous step in the elbow and wrist. At each step, model predictions are combined with the measured locations, where weights are based on the Kalman gain calculated on the estimated state error. Due to the incorporation of rigid body relations,

[figure not shown]

Fig. 2. Left: View of the subject's arm avatar and arm workspace for the VR training. Right: Therapist's control screen showing patient information and training parameters.

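### In Study 2 the arms differ by allocation in target progression as well as feedback, so a group difference cannot be credited to JEA feedback alone

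*Combined protocol and SAP*

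**What the plan says.** All references are to the combined protocol and SAP.

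- **Arms (Research plan).** "In both studies: Subjects will be randomly allocated to two equal groups". The contrast is then defined by feedback: "One group (control) will receive regular feedback and the other group will receive JEA feedback (randomized with catch trials". The section on subjects and recruitment repeats this definition.
- **Hypotheses (Research Objectives).** Hypothesis 1 is that JEA "will lead to better learning of movement speed and precision of a reaching task compared to no JEA", in healthy subjects and in patients with stroke. Hypothesis 2, for stroke, is that it "will lead to a greater increase in the patient's active control zone at the elbow compared to no JEA".
- **Progression (Training Protocol, game difficulty).** Target locations are altered "based on changes in active ranges for the JEA stroke group and by increments of 2 cm for the non-JEA group". Allowed movement time is also shortened. The trigger is common: "Difficulty will be progressed when the participant reaches a 90% success rate".
- **Extensions and tailoring (Research plan).** In the stroke group, "workspace extensions will be added as active range increases (i.e., exercise progression) for patients receiving JEA feedback". Also: "In the experimental group, target locations will be tailored to coincide with active control range limits determined at the beginning of each session".
- **Placement (For both studies: Training protocol).** The active workspace is measured for each session, and targets are shown inside it in both groups. The description of the robotic system adapts the stroke game to each patient's active range before every session. The motion-tracking text sets the targets from the subject's range of motion. Neither of these last two statements is restricted by arm.

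**The concern.** The hypotheses and the definition of the arms treat feedback as the only thing that differs. In the stroke study a second training component, the rule that moves the targets, is also assigned by arm. A control patient whose active range grows still progresses in 2 cm steps, while a JEA patient's targets follow the range.

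This matters most for Hypothesis 2. One component of the JEA regimen is driven by active range, and a Study 2 primary outcome is the area of the active control workspace, which is closely related to it. It matters for IP too, because training at different target distances is a plausible influence on reaching performance. The Knowledge translation section says that the results will mainly inform the design of a full randomised trial. The designers of that trial will need to know whether to carry forward JEA feedback, range-based progression, or both.

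**Working it through.** There is no planned figure to reproduce, because the question is which components differ by allocation. The check sets the arm-specific statements side by side.

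| Component (Study 2) | JEA arm | Control arm | Source |
|---|---|---|---|
| Feedback | JEA, with catch trials | Regular | Research plan |
| Target progression | Follows changes in active range | 2 cm increments | Training Protocol, game difficulty |
| Workspace extensions as range grows | Yes | Not stated | Research plan |
| Tailoring to range limits at session start | Yes | Not stated here | Research plan |
| Targets inside the measured workspace | Yes | Yes | For both studies: Training protocol |
| 90% trigger and shorter movement time | Yes | Yes (no arm restriction) | Training Protocol, game difficulty |
| Completion of 138 reaches per session | Yes | Yes (no arm restriction) | Training Protocol |
| Fixed-target Pre-, Post- and Follow-up Tests | Yes | Yes (no arm restriction) | Robotic system description |

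**What the design can identify.** Two components vary: feedback (JEA or regular) and progression (range-based or 2 cm). That gives 2 x 2 = 4 combinations. The trial studies 2 of them, JEA with range-based progression and regular feedback with 2 cm steps, with 12 patients each. Write F for the effect of feedback, P for the effect of the progression rule, and I for any interaction between them. The expected difference between the arms is F + P + I. It equals F only if P + I = 0, and the two arms contain no information on that. The Data analysis section compares changes in IP, workspace area and clinical scores. It has no arm or model term that separates F from P.

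**Is the rule only a consequence of JEA?** No. If JEA enlarged a patient's range and one rule then moved the targets in both arms, the further progression would be part of JEA's own effect. Here the rule itself is assigned, whatever happens to the range.

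**How wide is the extra contrast?** The statements on placement support a shared, range-based workspace: one says so for both groups, and two carry no arm restriction. Tailoring to the range limits in the experimental group is compatible with targets inside the workspace in both groups, though it may mean that JEA targets lie nearer the edge. What clearly remains is the progression rule and the JEA-only extensions.

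**Can the exposure be bounded?** Not usefully. A session lasts at least 30 minutes and is extended if needed to complete 138 reaches. If the interval between targets (2 to 10 s) and the 3 s reach add together, which is an assumption, the slowest schedule gives 1800 / (10 + 3) = 138.5 reaches. The 6 s midpoint gives 1800 / (6 + 3) = 200. So 138 is an approximate minimum per session, and multiples of it are not upper bounds. Zero progression is not a safe lower bound either. The 90% trigger governs game difficulty, but the JEA-only extensions and the tailoring at session start are not tied to it.

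**The case against.** The strongest reply is that the arms share nearly everything that matters: a workspace personalised to each subject, the trigger, the shortening of movement time, the minimum dose and the fixed-target tests. Most of this stands. A reader might infer from the tailoring sentence in the Research plan that controls get no range-based placement. The documents do not support that, since the section on training for both studies is explicit that targets lie within the measured workspace in both groups. The shared placement does not cancel the arm-specific progression rule or the JEA-only extensions.

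A second reply is that a personalised package was intended, since the introduction attributes the poor functional results of earlier error-augmentation studies to a lack of personalisation. That supports personalising training. It gives no reason for different rules by arm, and neither the arm definitions nor the hypotheses describe a package.

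A reader might also take the earlier trial in the introduction as evidence that range-based progression works. As described, that trial restricted reaching to the active zone. This concerns placement, which both arms here appear to share, and says nothing on range-based against 2 cm steps.

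Finally, this is a small preliminary study with a feasibility aim across two sites. That lowers the stakes, but it does not make the stated attribution correct.

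**Conclusion.** The concern holds for Study 2 and should be fixed. Target progression differs by allocation, so the trial compares two regimens and does not isolate JEA feedback. Hypotheses 1 and 2, as worded for stroke, claim more than the design can show.

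A reader might infer that the randomised comparison is invalid, or that it is biased in favour of JEA. Neither follows. The comparison of regimens as delivered is valid, and the size and direction of any effect of the progression rule cannot be computed from the documents. The effect could add to a JEA effect or mask one.

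The conclusion rests on taking the game-difficulty text at face value, supported by the separate statement on extensions in the Research plan. How far the contrast goes beyond the progression rule depends on whether the experimental group's tailoring to range limits differs from the placement described for both groups, which the documents leave open. The conclusion does not extend to Study 1, because the range-based progression rule names only the stroke JEA group. What applies to the healthy groups is at most a point to clarify.

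**What to change.** Before Study 2 training starts, choose one of two options.

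1. **One rule for both stroke arms (preferred).** For example, use range-based limits from the workspace measured for each session, with the same 90% trigger. Then align the Research plan, the section on training for both studies and the game-difficulty text, including the statements on tailoring and extensions. The active workspace is already measured for each session and the tonic stretch reflex threshold (TSRT) is already scheduled for the whole stroke group, so no new assessment is needed. The cost is a wording change and a game-setting change; the documents do not say how much work the latter takes.
2. **Keep the difference and name it.** Define the experimental intervention as JEA plus range-based progression, and reword the Study 2 hypotheses and conclusions to match. This costs wording only, but the later full trial would then not learn which component to carry forward.

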calculations of Kalman gains for elbow and wrist also account for shoulder and elbow error covariance respectively. Segment lengths are updated after each measurement step. Objects to be reached in VR are determined before training based on the subject's arm range of motion. The RANSAC algorithm (Fischler and Bolles 1981) is used to fit the recorded arm positions into the plane to reduce measurement errors.

Subjects and subject recruitment. Participants will be allocated by random numbers to either an *experimental group* that will receive JEA feedback (randomized with catch trials) or a *control group* that will receive no JEA feedback. **Blinding:** The sequence of allocation will be concealed from those assigning participants to groups until the moment of assignment, to prevent them from consciously or unconsciously influencing which participants are assigned to which groups. Participants will also be blinded to group allocation. Finally, evaluators will be blinded by concealing participant group allocation.

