Patients will be recruited through well-established procedures at the JRH. Potential participants will be identified from chart or database review and sent a letter of information describing the study. If they are interested, they will be directed to contact the research assistant by phone or email who will schedule them for a screening interview. Healthy subjects will be recruited from the community with the help of information flyers posted on bulletin boards. Subjects will participate after signing informed consent forms approved by the Center for Interdisciplinary Research in Rehabilitation (CRIR) Ethics Committee. Handedness will be measured for both studies with the Edinburgh Handedness Inventory (Oldfield 1971) but for Study 2, both right- and left-handed subjects will be included since hemispheric dominance is not expected to influence results. For Study 1, healthy women and men will be included who 1) are between the ages of 18-75 yrs; 2) have normal or corrected-to-normal vision; and 3) are able to provide informed consent. For Study 2, women and men will be included who 1) sustained a first cortical/sub-cortical ischemic/hemorrhagic stroke <1 yr previously and are medically stable; 2) are aged 18-75 yrs to minimize confounding effects of age-related changes in muscular responses; 3) are no longer receiving treatment; 4) have arm paresis (Chedoke-McMaster Arm Scale of 2-6 /7; Gowland et al. 1993) but are able to perform voluntary elbow movement of at least 30° per direction; 5) have mild-moderate elbow flexor spasticity; and 6) are able to provide informed consent. Subjects will be excluded if they have/are: 1) other major neurological neuromuscular/orthopaedic/pain problems that may interfere with task performance; 2) major cognitive deficits (<26 on Montreal Cognitive Assessment; Nasreddine et al. 2005) or 3) depression (> 14 on Beck Depression Inventory II; Beck et al. 1988; 1996).

[figure not shown]

Fig. 3. UL model based on the Kinect II skeleton (left) and explanation of the extended Kalman filter (right) to improve motion tracking accuracy.

Data analysis

For Study 2, data from Canada will be combined with those from Israel for a total of 12 subjects per group.

To address Hypothesis 1, we will compare the change in the IP between the Pre-Test and the Post-Test as an indicator of motor improvement and the change from Post-Test to Follow-Up as an indicator of motor learning using paired t-tests after verifying for data normality.

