To address Hypothesis 2, changes in the area of the active control workspace and clinical scores will be compared between groups using paired t-tests after verifying for data normality.

Knowledge translation

The preliminary results will primarily be used to inform the design of a full randomized controlled trial. However, preliminary results will be shared with clinicians at both sites and by oral or poster presentations at local, national or international meetings.

Participating researchers

[name] is a 1st year Master's student in the Integrated Program of Neuroscience at McGill University. **[name]** is Professor in the School of Physical and Occupational Therapy in the Faculty of Medicine at McGill University. She has pioneered many innovations in the area of upper limb rehabilitation, including identification of underlying motor control deficits at the joint and interjoint level, measurement of spasticity, incorporation of VR training interventions and the distinction between compensation and recovery. **[name]** is an Associate Professor in the Department of Industrial Engineering and Management at Ben-Gurion University of the Negev. She leads the Telerobotics laboratory where robotic motion control, learning, and interaction methodologies are developed and assessed. [name] has applied advanced mathematical methods for modeling and analysis of arm motion in healthy subjects and in patients with stroke. **[name]** is a Senior Lecturer in the Department of Physiotherapy who has been studying human movement in health and in disease for over a decade, publishing in journals that are either specific to neurological rehabilitation, or appropriate for inter-disciplinary research (e.g., in *Scientific Reports*). Profs. [name] and [name] have been collaborating on stroke rehabilitation for close to a decade. They have jointly published papers in leading journals and conferences [e.g., 15-17] and have worked together in two funded research projects. [name] and [name] have collaborated on robotic rehabilitation, and have jointly supervised a student working on robotic mirror-game treatment [18].

Budget and matching funds: details and justification

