The project is funded by an ABC (Agricultural, Biological and Cognitive Robotics) grant to [name] from Ben-Gurion University for the portion of the research done in Israel. Funds are allocated for supporting a scholarship or a graduate student. During the first year, most of the funds were allocated to the construction of the passive manipulator and purchase of equipment (i.e., computer, Montreal Spasticity Measure). Funds are allocated for subject compensation, publications and student travel to conferences.

Table 1. ABC budget Israeli team

Funding plan per fiscal year k US\$	Y - 1	Y - 2	Y - 3	Total
Scholarship for graduate student	2	2	2	

Building manipulandum + computer for the system	11		
Spasticity measurement equipment	9.5		
Supplies, peripherals, software license, Kinect, etc.	1	0.5	2
Human subject reimbursement	2		3
Travel: To Canada (year 2) Hosting in IL (year 1+3)	1	1	2
Student travel to conferences			3
Publications			3
Total k US\$	15	15	15
			45

Justification: Most of the budget in the first year is allocated to adapting the current robot/manipulandum and writing/implementing appropriate software for EA. Personnel costs are related to this activity in year 1 and to conducting the study in years 2 and 3. Human subject reimbursement (\$25 x 14 sessions (3 test + 10 training) x 12 subjects = 4200). Funds are allocated to defray travel costs to Israel in year 1 and 3 and hosting costs in Canada in year 2 for PI and students, as well as to defray costs of publication and presentation in years 2 and 3.

Table 2. Matching budget Canadian team

Matching funding is provided by [name] from the Canada Research Chairs fund (until March 2019) and then the Distinguished James McGill Professor fund.

Funding plan per fiscal year k US\$	Y - 1	Y - 2	Y - 3	Total
Personnel (Research assistant + engineer)	10			10
Personnel (Research assistant + student)		10	10	20
Adapting manipulandum, software + computer for the system	3			3
Supplies, peripherals, software license, Kinect, etc.				
Human subject reimbursement	2	2		4
Travel: To IL (year 1+3) Hosting in Canada (year 2)	2	1	2	5
Conference presentation and publications	2	1		3
Total k US\$	15	15	15	45

References

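### Study 2 pools two hospitals with no stated stratification by hospital and no site term; if the hospitals differ in mean change, the JEA comparison loses some precision (minor)

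*Combined protocol and SAP*

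**What the plan says.** All references are to the combined protocol and SAP.

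- **Size and sites.** The Research plan states that "we will test 24 healthy subjects and 24 patients who have moderate-to-severe stroke", and that "testing of patients will be done in two countries", at one hospital in Israel and one in Canada. The stated reason for two sites "is to assess the feasibility of conducting a multi-site study using this technology".
- **Allocation.** The Research plan says "Subjects will be randomly allocated to two equal groups". Subjects and subject recruitment adds: "Participants will be allocated by random numbers to either an" experimental or control group. Concealment is described. Stratification, blocking and the role of the hospital are not.
- **Analysis.** Data analysis says "For Study 2, data from Canada will be combined with those from Israel for a total of 12 subjects per group". For Hypothesis 2, "changes in the area of the active control workspace and clinical scores will be compared between groups using paired t-tests". For Hypothesis 1, changes in the index of performance (IP), which is also a Study 2 primary outcome, are examined by paired t-tests; that sentence does not say the test is between groups. Neither analysis has a site term.
- **Patients per hospital.** No planned number is given. The nearest figure is the Israeli budget line, "14 sessions (3 test + 10 training) x 12 subjects = 4200". Its 10 training sessions do not match the three in the current training protocol, so it is only a weak guide to the split.

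**The concern.** With 24 patients and one list that ignores hospital, the two arms can hold different shares of Israeli and Canadian patients by chance even when each arm has exactly 12. Stable differences between hospitals in level cancel in change scores. A difference in mean change does not cancel, and part of it then falls into the estimated JEA effect. The unadjusted t-test leaves that component in the error. Knowledge translation says the results will mainly inform the design of a full trial, and multi-site feasibility is the stated reason for having two hospitals, so how site is handled is within the study's purpose.

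**Working it through.** **The plan's own figure.** 2 × 12 = 24, which agrees with the text. The plan gives no power calculation, alpha, effect size or SD, so there is nothing further to reproduce.

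**Inputs.** From the documents: 24 patients, 12 per group, two hospitals. Assumed: 12 per hospital (8 and 16 as a check); two-sided alpha 0.05; normal change scores with within-hospital SD 1; a difference s between hospitals in mean change, in SD units, from 0 to 1. For power only, a true effect of 1.2 SD, chosen because it gives 80% power with 12 per group. The t-test is taken as a two-sample test, because the groups are different people.

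**1. Chance imbalance under one unstratified list with fixed 12:12 arms (hypergeometric).**
- 6:6 split: C(12,6)² / C(24,12) = 853,776 / 2,704,156 = 31.6%.
- 7:5 in either direction: 2 × 792² / 2,704,156 = 46.4%.
- 8:4 or worse: the remaining 22.0%.

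An 8:4 split moves the estimate by (8 − 4)/12 = 1/3 of s. That is 0.08, 0.17 and 0.33 SD at s = 0.25, 0.5 and 1, against a standard error of √(1/12 + 1/12) = 0.408 SD.

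**2. Average precision.** With 12 per hospital, the variance of the unadjusted difference over all allocations is 1/6 + s²/23. With stratification and a site term it is 1/6. Efficiency is therefore 1 / (1 + 6s²/23).

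| s (SD) | Efficiency | Loss, % of patients | Loss, of 24 |
|---|---|---|---|
| 0.25 | 0.984 | 1.6 | 0.4 |
| 0.5 | 0.939 | 6.1 | 1.5 |
| 0.75 | 0.872 | 12.8 | 3.1 |
| 1 | 0.793 | 20.7 | 5.0 |

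These figures do not depend on the treatment effect. With hospitals of 8 and 16 the multiplier 6 becomes 8 × 16/24 = 5.33, and the losses at 0.5 and 1 SD are 5.5% and 18.8%.

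**3. Power at the assumed 1.2 SD effect.** Exact noncentral t: 80.21% for the two-sample test when s = 0 (22 df), and 80.03% with stratification plus a site term (21 df), whatever s is. In simulation the unstratified t-test has about 79.5%, 77.5%, 74.5% and 70.5% at s = 0.25, 0.5, 0.75 and 1. A site term without stratification gives about 78% at every s, including s = 0.

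**4. Type I error.**
- One unstratified list, no site term: 4.9% to 5.0% throughout.
- Lists balanced within hospital, no site term: the true variance is 1/6, but the residual variance used by the test averages 1 + 6s²/22, which is 1.07 at s = 0.5 and 1.27 at s = 1. The test is too cautious: simulated type I error is 4.3% and 2.9%.
- Balanced lists plus a site term: 5.0% to 5.1%.

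**5. Break-even.** The fix gives the shorter interval once √(1 + 6s²/23) × 2.0739 (22 df) exceeds 2.0796 (21 df), that is, above about s = 0.15.

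**The case against.** **The hospital difference is hypothetical.** This stands. Nothing in the documents indicates one. Common eligibility criteria, a fixed 138 reaches per session, and a workspace expressed as a percentage of each patient's own biomechanical workspace all make a large one less likely. A reader might infer that pooling two countries biases the JEA effect or inflates false positives. The documents do not support that: allocation is random, and the error rate is at or below 5% under either reading of the allocation.

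**The allocation method may be better than it looks.** A reader might infer simple, coin-flip randomisation. The text does not say so, and equal groups argue against it, since 24 independent flips give exactly 12:12 only 16% of the time. Nor does the text say whether there is one list or one per hospital. If each hospital balances its own list, the 22% chance of an 8:4 split does not apply. The missing site term still matters, because the t-test is then conservative.

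**The power anchor is favourable to the point.** Partly right. At an assumed 0.5 SD effect, power is 21.6% at s = 0 and 20.8% at s = 0.5; at 0.8 SD it is 46.6% and 44.2%. The plan claims no power at all. The percent-of-patients figures avoid this choice.

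**The test itself is unclear.** Paired tests are named for a comparison of independent groups, and the IP sentence names no between-group test. That is a separate problem. For IP, this point applies only if a between-group comparison is intended. No site term appears under either reading.

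**Conclusion.** The point holds as a minor, low-cost improvement. It is well established that the plan states neither stratification by hospital nor a site term. The size of the consequence is less certain, because it depends wholly on an assumed between-hospital difference in change: negligible at 0.25 SD, small at 0.5 SD (2 to 3 power points at a 1.2 SD effect), and material only towards 0.75 to 1 SD, which nothing in the documents makes likely. The split of 12 per hospital is also assumed, though 8 and 16 gives similar results. The case for acting rests on asymmetry: about 0.2 power points lost if the hospitals are alike, against about 2, 5 and 9 points gained at 0.5, 0.75 and 1 SD.

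**What to change.** State whether allocation is by hospital. Randomise 1:1 within each hospital from concealed permuted blocks of varying size. Replace the Study 2 between-group t-test with a pre-specified linear model of change on group and site, and use it for IP as well if IP is to be compared between groups. Make both changes together: a site term alone costs about 2 power points when the hospitals are alike, and stratification alone leaves a conservative test. A fixed quota per hospital is not needed, so recruitment can stay competitive.

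Cost: two allocation lists instead of one; 1 df, taking power from 80.2% to 80.0% at an assumed 1.2 SD effect if the hospitals are alike; a possibly incomplete last block, and so arms not exactly 12:12, if one hospital recruits short; and slightly more predictable late assignments for staff who know earlier ones, which varying and undisclosed block sizes limit. No extra patients or visits are needed.
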